4.6 PACKAGING AND LABELING

4.6.1 Venetoclax

Venetoclax tablets will be packaged in high-density polyethylene plastic bottles to accommodate the study design. Each bottle will be labeled with the manufacturer name, address and telephone number, the protocol number, drug name, dosage form and strength (where applicable), amount of drug per container, lot number, expiration date (where applicable), medication identification/kit number, dosing instructions, storage conditions, and required caution statements and/or regulatory statements as applicable. Additional information may be included on the label as applicable per local regulations. A desiccant canister may be included in the bottle. If supplied with a desiccant, the desiccant canister should be returned to the bottle directly after each tablet removal.

For further details regarding venetoclax formulation, see the Venetoclax IB.

4.6.2 CC-486

CC-486 tablets will be packaged in blister cards. Each bottle will be labeled with the manufacturer name, address and telephone number, the protocol number, drug name, dosage form and strength (where applicable), amount of drug per container, lot number, expiration date (where applicable), medication identification/kit number, dosing instructions, storage conditions, and required caution statements and/or regulatory statements as applicable, including the warning, "Caution: New Drug — Limited by Federal (or United States) law to investigational use."

Only sufficient drug for one cycle of treatment will be provided to each subject at the start of each treatment cycle. All tablets should be swallowed whole, and should not be broken or chewed.

4.6.3 Obinutuzumab

Obinutuzumab is provided as a single 1000-mg dose liquid concentrate with a strength of 25 mg/mL. It is supplied in 50-mL glass vials containing 40 mL of the 25-mg/mL liquid concentrate. In addition to the antibody, the liquid also contains histidine/histidine-HCl, trehalose, poloxamer 188, and highly purified water which meets the specified limits according to Pharm. Eur. and USP.

4.7 RECEIPT OF DRUG SUPPLIES

Investigational agents will be received by the Investigational Drug Services (IDS) pharmacy at each participating site. The drug supply will be requested as each patient clears screening at each individual site. If subjects are assigned to a study cohort but withdraw prior to receiving drug, the tablets and vials will be returned to the supplying company or destroyed pending instructions from the supplying companies. When a new patient is assigned in replacement, supplies for the first cycle will be requested at that time.

4.8 PRODUCT STORAGE AND STABILITY

CC-486 tablets should be stored at 25 °C (77 °F), excursions permitted to 15 °C to 30 °C (59 °F to 86 °F). Venetoclax tablets must be stored at 15 °C-25 °C (59 °F - 77 °F). The recommended storage conditions for obinutuzumab drug products are between 2 °C and 8 °C, protected from light. For further instructions for obinutuzumab storage as well as information on in-use stability, see the packaging label. The storage area should be secure and have limited access.

4.9 DISPENSING OF STUDY DRUG

When a patient presents for a study visit at which oral investigational agents are to be dispensed (see Section 5 for a detailed schedule of drug dispensing), the IDS Pharmacy will be alerted of the patients' arrival with enough lead time to secure delivery of materials. The clinical investigation staff will have responsibility for the agent until it is given to the patient. The clinical investigation staff and patient will each mark receipt in a Drug Accountability Log. The number and strength of the tablets and/or capsules will be noted.

On days where study subjects are scheduled for obinutuzumab administration, the IDS Pharmacy representative will deliver the single full dose directly to the IV therapy nurse who will administer the drug to the patient.

Regular study drug reconciliation will be performed to document drug assigned, drug consumed, and drug remaining. This reconciliation will be logged on the drug reconciliation form, and signed and dated by the study team.

4.10 RETURN OR DESTRUCTION OF STUDY DRUG

At the close of the study, a detailed inventory of all remaining study drugs will be undertaken at all study sites. Any remaining study drugs will be returned or destroyed on site per instructions from the supplying companies.

5 STUDY PROCEDURES

5.1 Informed Consent

Study documentation including informed consent documents will be reviewed in detail and the potential subject given opportunity to ask detailed questions regarding the study. A schedule of events will be provided to the potential subject. If the subject elects to sign the informed consent documents and undergo screening, the assessments and procedures listed below with proceed.

5.2 VISIT 1: SCREENING

5.2.2 Screening Visit Methods and Procedures

The screening visit will take place in the oncology clinic space at participating trial sites. The visit must take place no more than 28 days prior to the planned initiation of therapy. A full medical history

will be obtained and recorded in the clinical record by the treating investigator or qualified designee, as well as detailed information about current medications, allergies, oncology treatment history, family history, social history and history of surgeries. Current symptoms will be elucidated and recorded in the clinical record.

5.2.3 Screening Visit Scales and Assessments

The treating investigator or qualified designee will take vital signs including temperature, pulse, respiratory rate, weight and blood pressure. Height will be measured at screening only. The body mass index (BMI) and body surface area (BSA) will be calculated.

- The Follicular Lymphoma International Prognostic Index (FLIPI) score (Solal-Céligny et al. 2004) will be assessed and recorded by the treating investigator or qualified designee (Appendix C).
- The treating investigator or qualified designee will assess ECOG status (Appendix B) at screening.
- A pretreatment whole-body PET scan will be obtained prior to the initiation of therapy.
- Formalin-fixed, paraffin-embedded slides and/or tissue block containing a tumor biopsy dated within 90 days prior to of the initiation of screening, or up to 28 days after screening initiation but prior to the start of therapy, will be obtained and sent to hematopathology at University of Chicago Medicine Hyde Park Campus for central pathology review (see Section 5.10 for instructions). The tumor biopsy material also will undergo next generation DNA sequencing of a targeted panel of cancer-related genes.
- Blood samples for correlative studies are to be provided to the main University of Chicago site for circulating methylation profiling and circulating tumor DNA analysis (see Section 5.10 for instructions).

5.2.4 Screening Visit Examinations and Questionnaires

The treating investigator or qualified designee will perform a complete physical exam during the screening period. Clinically significant abnormal findings should be recorded as medical history. The treating investigator or qualified designee may use standard intake forms to facilitate the collection of a detailed past medical history, family history, and medication list. These must be verified in a face-to-face encounter. No additional questionnaires are required.

5.2.5 Screening Visit Laboratory Studies

The following laboratory studies should be drawn within 28 days of the start of therapy:

- Complete blood count (CBC) with differential counts including hemoglobin, hematocrit, red blood cell count, mean corpuscular volume, white blood cell count, platelet count, absolute and relative neutrophil count, absolute and relative lymphocyte count, absolute and relative monocyte count, and absolute and relative eosinophil count.
- Complete metabolic panel including serum glucose, sodium, potassium, chloride, bicarbonate, blood urea nitrogen, creatinine, total protein, albumin, alanine transaminase, aspartate transaminase, and alkaline phosphatase.
- Serum uric acid level

- Serum lactate dehydrogenase level
- Serum beta-2 microglobulin level
- Prothrombin (PT) and activated partial thromboplastin (aPTT) times
- Hepatitis B core antibody (total)
- Hepatitis B surface antigen
- HIV 1/2 4th generation antibody and p24 antigen test
- Hepatitis C antibody screening
- A blood sample stored for testing if the patient develops a viral infection on study (e.g., cytomegalovirus, varicella zoster virus, herpes simplex virus, or Epstein–Barr virus).
- Pregnancy testing (see Appendix D for more details)

5.2.6 Screening Visit Medications

- a) Medications to begin:
 - TLS prophylaxis per Section 7.4.1.1. TLS prophylaxis should be continued at least through the end of Cycle 1.
 - o Infectious prophylaxis per Section 7.4.4.1
- b) Medications to discontinue (in cooperation with primary treating physicians):
 - Strong CYP3A4 inhibitors such as fluconazole, ketoconazole, and clarithromycin
 - Strong CYP3A4 inducers such as rifampin and carbamazepine

5.2.7 Plan for unscheduled visits

Study subjects will be provided with contact information for the clinic, including but not limited to access to the electronic health records messaging portal, business hour phone numbers for the clinic, and pager numbers for treating investigators. Study subjects will be provided with instructions to call for specific symptoms or any health concerns after the screening visits. Unscheduled visits may occur throughout the study period when concerns raised by patient contact or abnormal assessments indicate the necessity for such an encounter. Unscheduled visits may consist of laboratory draws only, a clinic visit, or an admission to an inpatient unit depending on the judgment of the treating investigator.

5.3 CYCLE 1 VISITS

Patients will be assessed and/or treated in the clinic at the appropriate study site on the following days during the 28-day Cycle 1:

- Day 1
- Day 8
- Day 15
- Day 22

Visits should ideally occur exactly on the scheduled date but are permitted to be rescheduled within a window of \pm 3 days.

5.3.1 Cycle 1 Methods and Procedures

Cycle 1 visits will take place in the oncology clinic space at participating trial sites. A focused medical history will be obtained and recorded in the clinical record by the treating investigator or qualified designee, as well as any changes in concomitant medical conditions, current medications, allergies, or social history. Current symptoms will be elucidated and recorded in the clinical record.

5.3.2 Cycle 1 Scales and Assessments

The treating investigator or qualified designee will take vital signs including temperature, pulse, respiratory rate, weight and blood pressure. The body mass index (BMI) and body surface area (BSA) will be calculated. The treating investigator or qualified designee will assess ECOG status (Appendix B) at each visit.

5.3.3 Cycle 1 Examinations and Questionnaires

The treating investigator or qualified designee will perform a focused physical exam during each visit. Clinically significant abnormal findings should be recorded as medical history. The treating investigator or qualified designee may use standard intake forms to facilitate the collection of changes in medical history, and medication list. These must be verified in a face-to-face encounter. No additional questionnaires are required.

5.3.4 Cycle 1 Laboratory Studies

On Days 1, 8, 15, and 22, the following studies should be obtained and reviewed prior to administration of any treatment scheduled for that day:

- Complete blood count (CBC) with differential counts including hemoglobin, hematocrit, red blood cell count, mean corpuscular volume, white blood cell count, platelet count, absolute and relative neutrophil count, absolute and relative lymphocyte count, absolute and relative monocyte count, and absolute and relative eosinophil count.
- Complete metabolic panel including serum glucose, sodium, potassium, chloride, bicarbonate, blood urea nitrogen, creatinine, total protein, albumin, alanine transaminase, aspartate transaminase, and alkaline phosphatase.
- Serum lactate dehydrogenase level.
- Serum uric acid level on Day 1 only, repeat as needed (see Appendix G)
- Serum beta-2 microglobulin level on Day 1 only.

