7.4.1 Tumor Lysis Syndrome

Tumor Lysis Syndrome, or TLS, is a known risk for patients with CLL who are treated with high cell killing agents, including venetoclax or obinutuzumab. TLS can be defined either by laboratory criteria or by clinical criteria following the guidelines of (Howard, Jones, and Pui 2011):

- Two of the following laboratory criteria must be present in serum studies in the same 24-hour window from the time of 3 days prior to therapy until 7 days after initial therapy:
 - \circ Uric acid > 8 mg/dL
 - Phosphorus > 4.5 mg/dL
 - o Potassium > 6 mmol/L
 - Corrected calcium < 7 mg/dL or ionized calcium < 4.5 mg/dL
- One of the following clinical criteria is sufficient to diagnose TLS in the 3 days prior to initial therapy or 7 days after initial therapy:
 - Cardiac dysrhythmia at least probably attributable to hyperkalemia
 - Cardiac dysrhythmia, seizure, neuromuscular irritability, hypotension or heart failure at least probably attributable to hypocalcemia
 - Acute kidney injury, defined by increase in serum creatinine level > 0.3 mg/dL from baseline, a single creatinine value > 1.5x the upper age-adjusted limit of normal, or oliguria defined as < 0.5 mL/kg/hr urine production for at least 6 hours

The risk of TLS is expected to be lower in FL than CLL based on prior studies of each agent individually (Davids et al. 2017; Marcus et al. 2017), but the exact nature of the risk of the combination in FL is unknown. Changes in blood chemistry consistent with TLS that require prompt management can occur as early as 6 to 8 hours following the first dose of venetoclax or obinutuzumab. The risk of TLS exists as a continuum based on multiple factors, including tumor burden and comorbidities. Risk is highest for those with bulky disease, elevated leukocyte count, elevated pretreatment LDH levels, compromised renal function, and dehydration. Perform tumor burden assessment with CT scan and CBC with WBC differential, assess blood chemistry (potassium, uric acid, phosphorus, calcium, and creatinine) in all patients and correct pre-existing chemistry abnormalities prior to initiation of treatment with venetoclax or obinutuzumab.

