On the day of the first administration of venetoclax and/or obinutuzumab, serial vital signs will be measured, and serum chemistry and hematology samples will be drawn before venetoclax and/or obinutuzumab dosing (see Appendix A). These samples are to be sent immediately to the laboratory and the treating investigator or designee must review the results promptly. Laboratory values obtained before the dose of venetoclax and/or obinutuzumab are to be used to determine whether a patient developed a change related to TLS. Additional laboratory studies including post-dose studies are up to the judgement of the treating investigator but are not required by the study protocol. Patients who develop electrolyte changes suggestive of TLS should undergo aggressive management and further monitoring per Appendix G.

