APPENDIX G: ELECTROLYTE IMBALANCES AND PREVENTION OF TUMOR LYSIS SYNDROME

Within the first 24 hours after the first dose or dose increase of any investigational agent in this protocol, if any laboratory criteria below are met, the patient should be hospitalized for monitoring and the investigator notified. No additional doses of investigational agents should be administered until resolution. Following resolution, investigational agents may be resumed following the dose modification guidelines in Section 4.2.2 and Section 4.2.3.

A rapidly rising serum potassium level is a medical emergency.

Guidelines for management are as follows:

- Nephrology (or acute dialysis service) must be consulted/contacted on admission (per institutional standards to ensure emergency dialysis is available).
- IV fluids (e.g., D5 1/2 normal saline) should be initiated at a rate of at least 1 mL/kg/h rounded to the nearest 10 mL (target 150 to 200 mL/h; not 50 mL/h). Modification of fluid rate should also be considered for individuals with specific medical needs.
- Monitor for symptoms or signs of TLS (e.g., fever, chills, tachycardia, nausea, vomiting, diarrhea, diaphoresis, hypotension, muscle aches, weakness, paresthesia, mental status changes, confusion, and seizures). If any clinical features are observed, recheck potassium, phosphorus, uric acid, calcium, and creatinine within 1 hour.
- Vital signs should be taken at time of all blood draws or any intervention.
- The management recommendations below focus on the minimum initial responses required. If a diagnosis of TLS is established, ongoing intensive monitoring and multi-disciplinary management will be per institutional protocols.

Specific recommendations:

Abnormality	Management Recommendations			
Hyperkalemia (including rapidly rising potassium)				
Potassium > 0.5 mmol/L increase from prior value (even if potassium within normal limits)	 Recheck potassium, phosphorus, uric acid, calcium, and creatinine in 1 hour. If further 0.2 mmol/L increase in potassium, but still upper limit of normal (ULN), manage per potassium ULN. Otherwise recheck in 1 hour. Resume per protocol testing if change in potassium is 0.2 mmol/L, and potassium ULN, and no other evidence of tumor lysis. At the discretion of the treating investigator, may recheck prior to hospitalization. If stable or decreased, and still WNL, hospitalization is at the 			

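### The lab schedule does not name every analyte that defines laboratory TLS, and it omits the Day 2 at-risk labs that 4.2.4 asks for (minor)

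*Combined protocol and SAP*

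**What the plan says.** **Definition and baseline.** Section 7.4.1 counts laboratory TLS when two of four criteria (uric acid, phosphorus, potassium, calcium) are met "in the same 24-hour window from the time of 3 days prior to therapy until 7 days after initial therapy". Before venetoclax or obinutuzumab is started, the same section tells sites to "assess blood chemistry (potassium, uric acid, phosphorus, calcium, and creatinine) in all patients". It also warns that TLS chemistry changes "can occur as early as 6 to 8 hours following the first dose of venetoclax or obinutuzumab".

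**Schedule.** In Cycle 1, section 5.3.4 draws labs on Days 1, 8, 15 and 22, before that day's treatment. The metabolic panel it lists includes potassium, creatinine and albumin but names neither calcium nor phosphorus. For uric acid it says "Serum uric acid level on Day 1 only, repeat as needed (see Appendix G". Section 5.5.4 repeats this list for Cycle 4, when the expansion cohort starts obinutuzumab, on Days 1, 8 and 15. The screening list in 5.2.5 and Appendix A name neither calcium nor phosphorus. Sections 5.3 and Appendix A allow 3 days either side of Day 8.

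**Post-dose labs.** Section 7.4.1.1 says: "Additional laboratory studies including post-dose studies are up to the judgement of the treating investigator but are not required by the study protocol". It adds: "Patients who develop electrolyte changes suggestive of TLS should undergo aggressive management and further monitoring per Appendix G". Section 7.4.1.3 gives hospitalised patients repeat labs at 8, 12 and 24 hours after venetoclax, and takes the chemistry panel from Section 5.2.4.

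**At-risk patients starting obinutuzumab.** Section 4.2.4 asks for labs on Days 1, 2, 8 and 15.

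**Use of the result.** TLS of any grade and any attribution is an adverse event of special interest (AESI) in 8.2.5, with expedited reporting under 8.3.2.

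**The concern.** Sites build their orders from Section 5 and Appendix A. A site that does so would have no named instruction to run phosphorus at any visit or calcium at any visit, and none to run uric acid routinely after dosing. It would also have no Day 2 draw, although 4.2.4 asks for one in at-risk patients.

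What is at stake is capture of a safety event. Section 7.4.1 itself says the exact TLS risk of the combination in FL is unknown, and 7.4 notes that venetoclax with obinutuzumab could lead to more TLS. If laboratory TLS in outpatients is found only when someone chooses to look, the reported count is a lower bound. It is also not comparable with the count in hospitalised patients, who are sampled three times in the first 24 hours.

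**Working it through.** There is no plan figure to reproduce. The check sets the definition against each scheduled draw.

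**1. Analytes at each draw, non-hospitalised patient**

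| Draw | Named in the visit list | If calcium comes with the panel |
|---|---|---|
| Day 1, pre-dose | potassium, uric acid: 2 of 4 | 3 of 4 |
| First 24 hours after dose | none scheduled: 0 of 4 | 0 of 4 |
| Day 8 | potassium: 1 of 4 | potassium, calcium: 2 of 4 |

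Day 1 becomes 4 of 4 if the site also carries out the pre-treatment chemistry in 7.4.1. The gap there is that the schedule does not list it.

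The definition needs two of four analytes, so there are 4 × 3 / 2 = 6 qualifying pairs. The named Day 8 tests can show none of them. With calcium added they can show one (potassium with calcium). A patient in whom only uric acid and phosphorus are raised would meet 7.4.1 without being detected from that draw. This counts coverage; it is not a detection rate.

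**2. Is the panel list closed?** Probably not. The lists in 5.2.5, 5.3.4 and 5.5.4 also omit bilirubin, yet Table 1 needs total bilirubin for eligibility and the liver-injury AESI in 8.2.5 uses it. So calcium probably comes with the panel, and the right-hand column is the likelier one. Nothing similar brings in phosphorus.

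**3. Timing.** With the first dose on Day 1, Day 8 is 7 days later. The permitted Days 5 to 11 are 4 to 10 days later:
- earliest: 4 × 24 = 96 hours
- nominal: 7 × 24 = 168 hours
- latest: 10 × 24 = 240 hours

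Days 9, 10 and 11, which are 3 of the 7 permitted days, fall after the 7-day limit of the definition.

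**4. Reflex route.** Section 7.4.1.1 sends patients with suggestive changes to Appendix G, where rechecks cover all four analytes. Something must start that route. Appendix G opens with "Within the first 24 hours after the first dose or dose increase of any investigational agent in this protocol", a period with no scheduled outpatient draw. If it is read as applying later too, a result such as "Potassium > 0.5 mmol/L increase from prior value" could start it from the Day 8 panel. A low calcium result alone could not, because that row also requires symptoms.

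**5. Day 2.** Section 4.2.4 asks for one Day 2 draw in at-risk patients. Sections 5.5 and 5.5.4 and Appendix A schedule none.

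**6. Cross-reference.** Section 5.2.4 covers examinations and questionnaires. The laboratory list is in 5.2.5, which names neither calcium nor phosphorus.

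**7. Cost of naming the analytes.** Day 1 phosphorus and calcium are already required by 7.4.1 and Day 1 uric acid is already listed, so the new assays are the Day 8 ones: phosphorus, calcium and uric acid, 3 per affected cycle. Expansion patients have two affected cycles (1 and 4) and dose-finding patients one. Section 3.1 gives 32 expansion and 12 to 18 dose-finding patients.
- Calcium new: 32 × 6 + 12 × 3 = 228, and 32 × 6 + 18 × 3 = 246.
- Calcium already on the panel, 2 per cycle: 32 × 4 + 12 × 2 = 152, and 32 × 4 + 18 × 2 = 164.

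These are upper bounds. Early discontinuation lowers them, and so does the provision in 6.2.2 that patients treated at the RP2D in dose finding count toward the 32.

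**The case against.** The strongest reply is that outpatient sampling is a stated, risk-adapted choice. Prophylaxis is mandatory before first venetoclax, all relevant chemistry is required before treatment, patients with defined bulky disease are admitted and sampled at 8, 12 and 24 hours, others may be admitted, and 7.4.1 expects lower TLS risk in FL than in CLL. Uric acid may be repeated as needed, and 5.2.7 allows unscheduled lab-only visits. This stands as a defence of not requiring intensive outpatient sampling. It does not explain why analytes that 7.4.1 requires in everyone before treatment are missing from the schedule, or why labs requested in 4.2.4 are absent from it.

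A reader might infer that laboratory TLS cannot be diagnosed in outpatients at all. The documents do not support that. The panel is probably open-ended, so potassium and calcium on Day 8 could satisfy the two-of-four rule. Pre-dose ascertainment is possible, and discretionary testing is allowed.

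A reader might also infer that missed laboratory TLS corrupts venetoclax dosing. Under 4.2.3, laboratory-only TLS that resolves within 48 hours leads back to the prior dose without adjustment, so missing a transient episode causes no dose-reduction error. Reduction requires laboratory TLS lasting longer than that, or clinical TLS.

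On Day 2, the specific rule in 4.2.4 can be read as governing over the general statement in 7.4.1.1. It is then a scheduling omission more than a contradiction, but a site working from the schedule would still miss the draw. The reference to 5.2.4 looks like a numbering slip. Correcting the number alone would still lead to a list without calcium or phosphorus.

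**Conclusion.** The point holds as a minor one. Phosphorus and calcium are required before treatment and are part of the TLS definition, but no scheduled panel names them. Uric acid has no routine post-dose draw in the TLS window, and the Day 2 at-risk labs are not on the schedule. The consequence is possible under-detection and under-reporting of laboratory TLS in non-hospitalised patients. Clinical TLS remains ascertainable, and neither the CR endpoint nor the handling of transient laboratory TLS under 4.2.3 is affected.

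The size can be given only as coverage: one named analyte of four at the first scheduled outpatient post-dose draw, or two if calcium is run, taken 96 to 240 hours after first dose. The documents give no TLS rate for this triplet, so no number of missed cases follows.

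Two assumptions matter. First, calcium probably comes with the panel, which is inferred from the bilirubin omission and not stated. Second, Cycle 4 is treated as a new TLS risk period in the expansion cohort. The window in 7.4.1 runs from initial therapy, so this is an interpretation; the at-risk prophylaxis and labs that 7.4.1.1 and 4.2.4 attach to starting obinutuzumab support it.

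**What to change.** 1. List phosphorus, calcium and uric acid on the Day 1 pre-dose and Day 8 draws of Cycle 1 in both cohorts, and of Cycle 4 in the expansion cohort. Take that Day 8 draw no later than Day 8, so that it falls inside the definition window.
2. Add the Day 2 draw for at-risk patients to 5.5.4 and Appendix A, with a matching exception in 7.4.1.1.
3. Point 7.4.1.3 to a panel that lists these analytes, in place of Section 5.2.4.
4. Report laboratory TLS separately for hospitalised and non-hospitalised patients. A Day 8 panel will not catch early transient changes, so the outpatient figure stays a lower bound even after items 1 to 3.

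The cost is about 3 new assays per affected cycle on blood already drawn: 228 to 246 in total, or 152 to 164 if calcium is already run. The Day 8 window loses its late side, so a lab-only visit is needed when the clinic visit slips past Day 8. The Day 2 draw for at-risk patients is a real visit, but 4.2.4 already asks for it. The rest is wording and one split in the safety tables. Sample size and error rates do not change.
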